#### 4.5.4 Harms

Adverse events will be summarised by MedDRA system organ class. Furthermore, adverse events and serious adverse events collected throughout the trial will be tabulated.

#### 4.5.5 Subgroup analyses

The following subgroup analyses were planned:

- by surgical specialty (as described in section 7.1.2);
- by ARISCAT score (26-44 vs. ≥45);
- according to whether patients were receiving an additional prehabilitation programme as part of usual care at their hospital.
- according to nutritional status at baseline (MUST score 0 vs MUST score >=1 and <2 vs MUST score> 2)
- according to physical activity status at baseline (DASI score <=median vs DASI score >
  median)
- according to depression/anxiety status at baseline (HADS score <=7 vs HADS score >7)

As the trial was halted early, these subgroup analyses planned in the protocol will not be performed. The primary outcome and progression of training load (secondary outcome) will be described by allocation within the subgroups for surgical specialty (cardiac vs. non-cardiac) and ATISCAT score (26-44 vs. ≥45).

#### 4.5.6 Further exploratory analyses

None

## 4.6 Missing data and outliers

A thorough data cleaning process will be carried out and attempts will be made to obtain any missing data by chasing until it is either received, confirmed as not available, or the study is at the analysis stage.

In all tables missing data for continuous variables will be indicated by footnotes. If the amount of missing data differs substantially between treatment groups potential reasons will be explored. The following strategy will only be applied to the primary outcome of the main study.

• If the proportion of missing data is less than 5% then complete case analysis will be performed (i.e., excluding cases with missing data).

• If the proportion of missing data is above 5% multiple imputation methods will be considered. A general imputation model that uses an iterative procedure to generate imputed values will be used to generate multiple complete data sets (e.g., using Stata's mi impute). The model of interest will be the fitted to each of the complete data sets and effect estimates combined using Rubin's rules. If appropriate, methods such as predictive mean matching will be used in order to ensure that imputed values lie within specific ranges.

## 6. Glossary

Acronym	Details
AE	Adverse event
ARISCAT	Assess respiratory risk in surgical patients in Catalonia
CI	Confidence interval
CRF	Case report form
DSMC	Data safety monitoring committee
GMR	Geometric mean ratio
HR	Hazard ratio
ICH-GCP	International conference for harmonisation of good clinical practice
IQR	Inter quartile range
ITT	Intention to treat
MDT	Multidisciplinary team
MedDRA	Medical dictionary for regulatory activities
MIP	Maximal inspiratory pressure
PIL	Patient information leaflet
RCT	Randomised controlled trial
SAE	Serious adverse event

SAP	Statistical analysis plan
SD	Standard deviation
SOP	Standard operating procedure

## 7. Revision history

Version 1.0 of the SAP should be signed off by relevant personnel before any data analysis is carried out. If changes need to be made to v1.0 before this time, possibly due to emerging methodologies, these changes should be documented in Table 1 below, with new version number, date and a summary of the changes with justification(s). If any changes to the methodologies are required after data analysis has begun, these should be documented in the final analysis report in a chronological manner, documenting all decisions made and their justification(s).

**Table 1 SAP revision history** 

Version number	Revision date	Justification for revision

## **APPENDIX A: Skeleton tables and figures**

The following summarises the planned outputs:

Section	Outputs							
Section 1	Tables and figures detailing study population							
Population	Figure A1	Flow of participants						
	Figure A2	Predicted and actual recruitment						
	Table A3	Screening details						
	Table A4	Withdrawals						
Section 2	Summary ta	bles of demographic and surgical information						
Baseline,	Table A5	Baseline demographic and clinical characteristics						
randomisation and surgical data	Table A6	Other baseline data						
Surgical data	Table A7	Day of surgery clinical measures and operative details						
	Table A8	Protocol deviations						
	Table A9	Randomisation and intervention timings						
Section 3	Summary da	ita and treatment estimates for primary and secondary outcomes						
Primary and	Table A10	SWAT primary and secondary outcomes						
secondary outcome data, and adverse	Table A11	Primary and secondary outcomes						
events	Table A12	PPC and progression in training load, within surgical specialty and ARISCAT score						
	Table A12	Adverse events and serious adverse events- in hospital						
	Table A13	Adverse events and serious adverse events -during follow-up						

Figure A1: Patient flowchart

[figure not shown]

Figure A1: Predicted and actual recruitment

[figure not shown]

Table A3: Screening details

	Car	diac	Non-cardiac		Ove	rall
Reasons for ineligibility	n	%	n	%	n	%
<18 years of age						
Undergoing emergency surgery						
Not having elective major cardiac, thoracic or abdominal surgery						
ARISCAT score <26			·  			
<14 days until planned operation date			·  			
Unable to provide informed consent			·  			
Unable to participate in the intervention			·  			
Recent cardiac, thoracic or open abdominal surgery (in previous two months)						
Prisoners						
History of spontaneous pneumothorax						
Eardrum perforation within previous six weeks						
Phrenic nerve palsy		ļ				

## **Table A4: Details of withdrawals**

Centre	Specialty	Timing of withdrawal	Reason for withdrawal

## Section 2: Baseline and surgical data

## Table A5: Baseline demography

		Treatmen	t A (n=XXX)	Treatment	B (n=XXX)	Treatment	C (n=XXX)	Overall (n=XXX)	
		n	%	n	%	n	%	n	%
BASELINE CHARA	CTERISTICS								
Sex	Females								
Age – mean (SD)									
BMI – mean (SD)									
Ethnicity	White or Caucasian								
	Black/Black British								
	Mixed/Multiple ethnic								
	groups								
	Asian/Asian British								
	Other ethnic group								
Type of surgery	Cardiac								
	Thoracic								
	Abdominal								
GENERAL COMOR	RBIDITIES								
Diabetes	No								
	Insulin								
	Oral								
	Diet								
Ischaemic heart dise	ease								
Myocardial infarction	n within 6 months								
Heart failure									
Hypertension requir	ing treatment								
Peripheral vascular									
Stroke									
TIA									
Liver disease (exc c	irrhosis)								
Cirrhosis	·								

		Treatment	A (n=XXX)	Treatmen	Treatment B (n=XXX)		C (n=XXX)	Overall (n=XXX)	
		n	%	n	%	n	%	n	%
Renal disease	Stage 1								
	Stage 2								
	Stage 3a								
	Stage3b								
	Stage 4								
	Stage 5								
Condition associate	d with immunosuppression								
Immunosuppress	sant drugs								
Long-term steroi	ds								
	previous 6 months								
RESPIRATORY CO	DMORBIDITIES								
Asthma									
If yes, any hospi	tal admissions in last 6 months								
Chronic pulmonary	disease								
If yes, any hospi	tal admissions in last 6 months								
Interstitial lung disea	ase								
If yes, any hospi	tal admissions in last 6 months								
Pulmonary hyperter	nsion								
If yes, any hospi	tal admissions in last 6 months								
Bronchiectasis									
If yes, any hospi	tal admissions in last 6 months								
Obstructive sleep a	pnoea								
If yes, any hospi	tal admissions in last 6 months								
If yes, CPAP?									
If yes, any hospita	al admissions in last 6 months								
COVID-19 (test con	firmed)								
If yes, any hospi	tal admissions in last 6 months								
SMOKING STAT	US								
Smoking	Non-smoker								
3	Ex-smoker >3								
	months								

		Treatment	A (n=XXX)	Treatmen	Treatment B (n=XXX)		C (n=XXX)	Overall (n=XXX)	
		n	%	n	%	n	%	n	%
	Ex-smoker <3mths								
	>14days								
	Current smoker								
Number of years par									
Number of cigarette									
Number of cigars pe									
Number of pipes per									
Number of "other" pe	er day								
E-cigarettes									
CANCER / MALIGN	IANCY								
Surgery for cancer									
Primary or secondary tumour	Primary								
- -	Secondary								
Site of malignancy	Lung								
	Oesophagus								
	Stomach								
	Colon								
	Rectum								
	Anus								
	Gall bladder								
	Biliary tree								
	Pancreas								
	Liver								
	Kidney								
	Bladder								
	Endometrium/Ovary								
	Other								
Curative or calliative	Curative								
	Palliative								
	Don't know								

	Treatment A (n=XXX)		Treatment	B (n=XXX)	Treatment	C (n=XXX)	Overall	(n=XXX)
	n	%	n	%	n	%	n	%
Neo-adjuvant treatment in 6 months								
If yes, radiotherapy								
If yes, chemotherapy								
If yes, immunotherapy								
ARISCAT								
ARISCAT score – median (IQR)								
26-44								
>44								
Receiving an additional prehabilitation programme as part of usual care								
Nutritional status MUST score 0								
MUST score 1-2								
MUST score >2								

Table to be repeated with participants grouped by surgical specialty (cardiac vs non-cardiac) and grouped by SWAT randomised allocation

**Table A6: Baseline questionnaires** 

		Treatment A	Treatment B	Overall
BASELINE QUE	BASELINE QUESTIONNAIRES			
EQ-5D	Median (IQR) score			
SF-12	Median (IQR) score			
HADS	Median (IQR) score			
CRQ	Median (IQR) score			
Self-efficiency	Median (IQR) score			
DASI	Median (IQR) score			

Note instruments provide more than one summary score, table is for illustrative purposes

Table A7: Day of surgery clinical measures and operative details

			ment A XXX)		nent B (XX)		nent C XXX)	Ove (n=)	
		n	%	n	%	n	%	n	%
DAY OF SURGER	RY								
ROUTINE CLINIC	AL MEASURES								
Pre-operative SpC	02 on admission								
Prescribed an anti infection	ibiotic for a respiratory								
BLOOD TEST RE	SULTS								
Haemoglobin									
eGFR									
Creatinine									
Albumin									
ASA PHYSICAL S SYSTEM	STATUS CLASSIFICATION								
ASA score									
OPERATION DET	TAILS								
Open									
Laparoscopic / Minimally invasive									
OPCS code									
Primary incision made	Intrathoracic								
mado	Abdominal								
	Peripheral								
Estimated blood loss									
INTRAOPERATIV	/E VENTILATION								
Maximum positive end									
expiratory pressure (PEEP)									
Maximum tidal									
volume (SetTV)									
Maximum FiO2 intraoperatively									
(excluding during									
induction)									

**Table A8: Protocol deviations** 

	Cai	rdiac	Non-c	ardiac	Ove	erall
	n	%	n	%	n	%
Non-adherence to the intervention						
Intervention not delivered per protocol						
Less than 2 weeks IMT training						
More than 8 weeks IMT training						
Missed all training						
More training than recommended (>2x 15min sessions/d)						
Continue training after surgery						
Not training at the recommended intensity (high resistance IMT group only)						
Other monitoring of study intervention						
Undergone surgery prior to completing the intervention						
Surgery delayed because of intervention						
Other non-compliance						
Ineligible but randomised						
Did not receive allocated intervention (cross- over)						

Table to be repeated with participants grouped by randomised allocation

Table A9: Details on randomisation and intervention timings

	Car	diac	Non-c	ardiac	Overall		
	n	%	n	%	n	%	
Days between randomisation and surgery (Median, IQR)							

Table to be repeated with participants grouped by randomised allocation

Section 3: Primary and secondary outcomes

Table A10: SWAT primary and secondary outcomes

		Automatic load + Additional visit (n=XX)	Manual load + Additional visit (n=XX)	Automatic load + No additional visit (n=XX)	Manual load + No additional visit (n=XX)
PRIMARY OUTC	OME				
Training load	Baseline				
	Day of surgery*				
	Change from baseline				
SECONDARY OL	ITCOMES				
Work	Baseline				
	Day of surgery*				
	Change from baseline				
MIP	Baseline				
	Day of surgery				
	Change from baseline				
FEV 1	Baseline				
	Day of surgery				
	Change from baseline				
FVC	Baseline				
	Day of surgery				
	Change from baseline				

Inspire SAP, version v0.3 05/07/2024
In accordance with v3.0 of the study protocol

Proportion of participants following at least 80% of the planned training sessions

Recorded on patient diary

Recorded on KHP2 device

Proportion of participants training at the prescribed intensity score of (RPE rating )

First, second and last line of patients diary

Most recent 10 sessions at additional visit

(participants randomised to additional visit only)

Table A11: Primary and secondary outcomes

Outcome	Randomised to IMT (n=xx)	Randomised to Sham IMT/Usual care (n=xx)	Randomised to Sham IMT (n=xx)	Randomised to usual care (n=xx)	Effect (95% CI)*	p-value
Any PPC					RD/RR	
Respiratory infection					-	-
Respiratory failure					-	-
Pleural effusion					-	-
Atelectasis					-	-
Pneumothorax					-	-
Bronchospasm						
Aspiration pneumonitis					-	-
Invasive ventilation					-	-

Inspire SAP, version v0.3 05/07/2024

In accordance with v3.0 of the study protocol

\* Measurement taken from last line of patients diary. This was on day of surgery for XX participants, within 2 days of surgery for XX participants, within 3-7 days for XX participants and within >7 days for XX participants

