- 1. **High resistance IMT.** Participants will be given a device and taught to do the IMT using the hand held device and instructed to train twice per day (30 breaths each time) for a minimum of two weeks. Participants will be taught to increase the load resistance on their device based on their breathing effort which they will self-assess using a scale. If they have a longer wait, they can continue doing the exercises until the operation.
- 2. **Low resistance IMT.** Participants will do the same as for the high intensity group, but the device will be set to a training load that will not change the strength or endurance of the inspiratory muscles. It is important that participants in this group believe that they are actually training, as the aim of this group is to account for any "placebo" effect, thereby ensuring that any reduction in lung complications in the high intensity group is "real".
- 3. **Usual care.** Participants will be given advice about the importance of deep breathing exercises and a leaflet instructing them how to do these exercises, but will otherwise have no additional breathing training before surgery.

The clinical team looking after patients at the time of surgery will not know to which group a patient has been allocated. We will measure the strength of the inspiratory breath when a

patient agrees to take part and immediately before the operation in all three groups, so that we can determine which type of breathing exercises work. In the high and low resistance IMT groups, we will monitor how much training patients were able to complete in the two weeks prior to surgery by asking them to complete a diary of their training (the number of training sessions and duration of each session is recorded automatically on the device).

The main aim of the study is to compare the number of lung complications between the three groups in the first 30 days after surgery. We will record whether a lung complication develops in hospital whilst patients are recovering from surgery or causes hospital admissions after patients are discharged from hospital following their operation. We will also compare the time patients spend in hospital, their quality of life after their operation and survival.

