#### 5.6.4.2 Low resistance IMT training protocol

Participants in the low resistance IMT group will undertake 30 breaths, two times daily, 7 days per week, using the POWERbreathe® KHP2 at home. The training load will be set at 10% of MIP, and will remain at this level throughout. Training will continue for a minimum of two weeks and can continue until the day of surgery. Participants will also be given a usual care leaflet containing advice on deep breathing exercises.

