# 6.4 Duration of treatment period

The duration of the treatment commences when the participant receives face to face training on breathing exercise regimens in all three arms; high resistance IMT, low resistance IMT or usual care. The duration of the breathing exercises will be for a minimum of two weeks before the day of surgery. In some instances the surgery date may be cancelled or postponed; in such instances, the duration of treatment will be extended further until an alternative surgery date is confirmed. For non-cancer surgery (e.g. elective heart surgery), the waiting time between referral for surgery and surgery may be longer than 2 weeks; therefore, participants will be recruited as soon as feasible and may be required to perform the intervention for up to 8 weeks before the day of surgery.

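### SAP Table A8 counts all IMT training past 8 weeks as a deviation, although protocol v2.0 extends training when surgery is postponed; separately, the NO branch of the adherence rule has a reversed inequality (minor)

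*SAP*

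**What the plan says.** **Deviation table.** SAP Table A8 lists "More than 8 weeks IMT training" among the protocol deviations, with columns for cardiac, non-cardiac and overall, to be repeated by randomised allocation. The row carries no exception or footnote. The first row of the table is "Non-adherence to the intervention", and a row on delivery of the intervention stands between it and the duration rows.

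**Protocol on duration.** Protocol v2.0, section 6.4, sets a minimum of two weeks. For cancelled or postponed surgery it says "the duration of treatment will be extended further until an alternative surgery date is confirmed". The next sentence is the evident source of the 8-week figure. It begins "For non-cancer surgery (e.g. elective heart surgery), the waiting time between referral for surgery and surgery may be longer than 2 weeks" and goes on to say that participants "may be required to perform the intervention for up to 8 weeks before the day of surgery". Section 5.6.4.2, on the low resistance arm, reads "Training will continue for a minimum of two weeks and can continue until the day of surgery". The trial summary, describing the high resistance arm, reads "If they have a longer wait, they can continue doing the exercises until the operation".

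**Adherence variable.** In SAP 4.3.2, under adherence to inspiratory muscle training, YES needs one or more sessions on five or more days a week, kept up for two weeks or longer, and 30 or more breaths on each day. There is no maximum duration. The second list of conditions, which is the NO branch, ends with the same requirement of 30 or more breaths, joined by OR.

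**Per-protocol set.** SAP 3.3.2 makes a per-protocol analysis of the primary outcome optional, to be considered if major deviators exceed 5% of the ITT population. It names two deviation types, ineligibility and failure to receive or adhere to the intervention, and refers to Table A8 for the counts.

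**Versions.** The SAP is v0.3 and is marked "In accordance with v3.0 of the study protocol". The protocol available here is v2.0.

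**The concern.** The row takes the 8-week figure from protocol 6.4 but leaves out the extension that the same paragraph orders when surgery is postponed. A participant who keeps training because the operation was moved is doing what the protocol asks, and is then reported as having departed from it.

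This matters mainly for reporting. The trial was halted, secondary outcomes will only be tabulated, and adherence is a stated aim of the pilot (SAP 2.1.1). Table A8 is split into cardiac and non-cardiac, and protocol 6.4 gives elective heart surgery as its example of longer waits. The row would therefore probably inflate the cardiac deviation count. Table A9 shows only the days from randomisation to surgery, so no planned output tells the reader which long durations came from postponement.

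A second possible consequence is for the per-protocol set. If Table A8 rows were used to define it, compliant participants could be removed, and only from the IMT arms.

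The breath condition is a separate drafting error, but it sits in the variable that carries the pilot's adherence aim.

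**Working it through.** **1. One case under each rule.** The durations are assumed. Surgery planned for week 6 is postponed to week 10, and the participant trains twice daily, 7 days a week, 30 breaths a session, until surgery.

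| Rule | Test | Result |
|---|---|---|
| Protocol v2.0, 6.4 | surgery postponed, training extended | compliant |
| SAP 4.3.2, YES branch | 7 ≥ 5 days a week; 10 ≥ 2 weeks; 2 × 30 = 60 ≥ 30 breaths | adherent |
| SAP Table A8 | 10 > 8 weeks | deviation |

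The conflict is between the first and third lines. It arises for any duration above 8 weeks that is reached through postponement or cancellation.

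**2. The NO branch.** The same participant, with 60 breaths a day, also meets the last NO condition, because it too asks for 30 or more. Conversely, a participant who trains on enough days for enough weeks but takes fewer than 30 breaths fails YES and meets none of the NO conditions, so falls to MISSING. With the inequality reversed, the first is YES only and the second is NO.

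**3. Number misreported.** The documents do not give the number recruited, or the share g of IMT participants taken past 8 weeks by postponement or cancellation. Both are assumed. Take N = 321 (the Phase 1 projection, SAP 2.1) and 2:1:1 allocation, so three quarters are in IMT arms: 0.75 × 321 = 240.75. The 5% trigger is 0.05 × 321 = 16.05 participants.

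| g | Listed (g × 240.75) | Share of all (0.75g) |
|---|---|---|
| 2% | 4.8 | 1.5% |
| 5% | 12.0 | 3.75% |
| 10% | 24.1 | 7.5% |

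The row alone passes the trigger only if g > 0.05/0.75 = 6.7%. Ordinary non-adherence could pass it regardless: the progression criterion in SAP 2.1.3 tolerates 30% of IMT participants, which is 0.30 × 0.75 = 22.5% of all.

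**4. Per-protocol shift if all of them were excluded.** Assume no true effect and the same g in each arm. Let D be the PPC risk in these patients minus the risk r in the rest. Each arm has overall risk r + gD. After exclusion the high resistance arm has risk r. The combined comparator has low resistance patients (weight 1 − g) at risk r and usual care patients (weight 1) at r + gD, giving r + gD/(2 − g). The risk difference therefore moves by −gD/(2 − g).

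| Size of shift (points) | g = 2% | g = 5% | g = 10% |
|---|---|---|---|
| D = 5 points | 0.05 | 0.13 | 0.26 |
| D = 10 points | 0.10 | 0.26 | 0.53 |

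The sign reverses with the sign of D, which is unknown.

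**5. Scale.** With the planned PPC risk of 20% and 160.5 participants on each side, the 95% half-width is 1.96 × √(0.2 × 0.8 × 2/160.5) = 8.75 points. The largest shift shown is 0.53/8.75, about 6% of that.

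**The case against.** **The 8-week figure has a basis.** Protocol 6.4 does say up to 8 weeks for non-cancer waits, and the wording in 5.6.4.2 and the trial summary is permissive. Recording longer training is defensible. This stands, and it limits the clear conflict to postponed or cancelled surgery. A reader might infer that everyone above 8 weeks is wrongly listed; the text does not go that far.

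**Adherent and deviating are not opposites.** The adherence variable is a minimum-dose rule and Table A8 is a log of departures. Table A8 also lists training more than recommended and training after surgery, neither of which the adherence rule caps. This stands too. Meeting the adherence rule while appearing in Table A8 is not in itself a contradiction, and adherence by specialty (SAP 4.5.3) need not change because of this row.

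**The row may not belong to non-adherence.** With the indentation lost in extraction, the parent of the duration rows is uncertain. That such patients are labelled non-adherent is likely but not established. That they are labelled deviators is certain from the table's title.

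**The per-protocol effect is conjectural.** The analysis is only to be considered, the SAP does not say which rows are major, and Appendix A plans no per-protocol output. A reader might infer that compliant patients will be excluded and the result biased; the SAP does not say so.

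**Protocol v3.0 may differ.** Delivery did change: the face-to-face visit in v2.0 appears in the SAP as a virtual meeting. Section 6.4 may have changed as well. This cannot be settled from the documents available.

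**Conclusion.** The point holds in limited form and is minor. Against protocol v2.0, Table A8 would misreport as deviators those participants who trained past 8 weeks because surgery was cancelled or postponed. It affects the IMT arms only, and probably cardiac patients more; the latter is inferred from the example in 6.4, not from data.

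On the assumed 321 participants, shares of 2% to 10% give about 5 to 24 people. The percentages and the shift formula do not depend on N. SAP 1.1.2 reports slower recruitment, and a smaller N would widen the interval further. A material per-protocol bias is not supported: even if every such participant were excluded, the shift is about 0.05 to 0.53 points for the assumed values of g and D, in an unknown direction. The ITT analysis includes all randomised participants and does not change.

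The reversed inequality in the adherence rule is an error on its face and does not depend on the protocol version or on any assumption.

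**What to change.** Check section 6.4 of protocol v3.0 first. Then, before SAP v1.0 is signed off:

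- **Table A8.** Limit the row to training beyond 8 weeks that postponed or cancelled surgery does not explain. Alternatively, move it out of the deviation table and report training duration descriptively beside Table A9.
- **SAP 3.3.2.** State that training extended for this reason is not a major deviation and does not count towards the 5% trigger.
- **SAP 4.3.2, adherence variable.** Change the breath condition in the NO branch to fewer than 30.

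The cost is wording in a SAP that is still at v0.3. The ITT analysis does not change and no participant is newly excluded. Applying the exception needs the reason for a long wait; if that was not recorded, the descriptive row is the simpler choice.
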